9.2 Variable Definitions

Primary and secondary efficacy variables as well as exploratory and safety outcomes are described in the table below.

Note that for any patient who had a repeat baseline, their repeat measures will be used in the definition of baseline (their updated baseline scores were entered into the repeat baseline CRF by the sites).

Variable	Туре	Definition
Primary Outcomes		
type of urinary incontinence	Categorical stress-predominant urgency-predominant balanced	 The definition of the type of urinary incontinence will be based on 2 questions of the Urogenital Distress Inventory, 1. "Do you experience urine leakage associated with a feeling of urgency?" 2. "Do you experience urine leakage related to physical activity, coughing, or sneezing?" Based on our inclusion criteria, patients must report at least "moderate" bother on both questions. If the subject reports greater bother on the stress question, she will be classified as stress-predominant MUI. If the subject reports greater bother on the urgency question, she will be classified as urgency-predominant MUI. If the subject reports equal bother on both questions, she will be classified as "balanced" MUI.
Change from baseline in UDI Total Score at 6 months (and at 3, 9, and 12 months) 6 months is primary,	Continuous	The Urogenital Distress Inventory-Total Score will be computed at baseline and 6 months (and 3, 9, and 12 months) using the standard scoring algorithm. Specifically, the instructions are to sum the Stress, Irritative, and Obstructive subscales of the UDI (see below). If any subscale scores are missing, then the score will be calculated as the sum of the non-missing scales. The outcome will then be computed as the difference in Total score at 6 months (and 3, 9, and 12 months) and the Total score at baseline. If data for an assessment time point are missing, the outcome variable will be coded as missing.

Variable	Туре	Definition
Secondary Outcomes		

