Change from baseline in UDI Obstructive Score at 6 months (and at 3, 9 and 12 months)	Continuous	The Urogenital Distress Inventory-Obstructive Score will be computed as baseline and 6 months (and 3, 9, and 12 months) using the standard scoring algorithm. Specifically, the instructions are to average responses across questions E, J, K, L, M, N, O, P, Q, R, and S and their respective sub-questions (0=No or Yes and Not at all; 1=Yes and Slightly; 2=Yes and Moderately; 3=Yes and Greatly), and then multiply by 100/3. If any responses are missing, then the score will be calculated as the average of the non-missing responses. The outcome will be computed as the difference in score at 6 months (and 3, 9, and 12 months) and the score at baseline. If data for an assessment time point are missing, the outcome variable will be coded as missing.
Change from baseline in UDI Stress Score at 6 months (and at 3, 9 and 12 months)	Continuous	The Urogenital Distress Inventory-Stress Score will be computed at baseline and 6 months (and 3, 9, and 12 months) using the standard scoring algorithm. Specifically, the instructions are to average responses across questions D and F and their respective sub- questions (0=No or Yes and Not at all; 1=Yes and Slightly; 2=Yes and Moderately; 3=Yes and Greatly), and then multiply by 100/3. If any responses are missing, then the score will be calculated as the average of the non-missing responses. The outcome will then be computed as the difference in score at 6 months (and 3, 9, and 12 months) and the score at baseline. If data for an assessment time point are missing, the outcome variable will be coded as missing.
Change from baseline in UDI Irritative Score at 6 months (and at 3, 9 and 12 months)	Continuous	The Urogenital Distress Inventory-Irritative Score will be computed at baseline and 6 months (and 3, 9, and 12 months) using the standard scoring algorithm. Specifically, the instructions are to average responses across questions A, B, C, G, H, and I and their respective sub-questions (0=No or Yes and Not at all; 1=Yes and Slightly; 2=Yes and Moderately; 3=Yes and Greatly), and then multiply by 100/3. If any responses are missing, then the score will be calculated as the average of the non-missing responses. The outcome will then be computed as the difference in score at 6 months (and 3, 9, and 12 months) and the score at baseline. If data for an assessment time point are missing, the outcome variable will be coded as missing.

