Change from Baseline OAB- q HRQL Total Score at 3, 6, 9, 12 Months		The OAB-q HRQL Total Score will be computed at baseline and 6 months (and 3, 9, and 12 months) using the standard scoring algorithm. Specifically, instructions are to sum the OAB-q HRQL Coping, Concern, Sleep, and Social prior to subtracting from the respective maximum possible scores, then subtract from the maximum possible sum score (150) and divide by the range of possible scores ((18+42+30+10=150)-(8+7+5+5=25)=125), then multiply by 100. The outcome will then be computed as the difference in score at 6 months (and 3, 9, and 12 months) and the score at baseline. If any of the listed subscales are missing, the Total score will also be set to missing. If data for an assessment time point are missing, the outcome variable will be coded as missing.			
OAB-SAT-q Satisfaction Score at 3, 6, 9, 12 Months	Continuous	 NOTE: The scoring manual for the OAB-SAT-q states that higher scores should correspond to better outcomes and details that final composite scores for each dimension should be obtained by subtracting raw scores from the highest possible score and dividing by range. However, based on the direction of score for individual responses, this derivation would result in lower scores corresponding with better outcomes. We have adjusted the scoring algorithm instead to be: 100*(raw score – lowest possible score)/score range. This calculation results in higher scores corresponding to better outcomes and an overall scale of 0-100. The OAB-SAT-q Satisfaction Score will be computed at 6 months (and 3, 9, and 12 months) using the standard scoring algorithm. Specifically, instructions are to sum responses across questions 1, 2, and 3 (1=Extremely Dissatisfied,, 6=Extremely Satisfied), then subtract the lowest possible score (3) from the raw score and divide by the range of possible scores (18-3=15), then multiply by 100. If less than half of the 			

Variable	Туре	Definition				
		responses are missing, then the score will be calculated by substituting the missing responses with the average of the non-missing responses, otherwise no score is calculated. If data for an assessment time point are missing, the outcome variable will be coded as missing.				

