Change from Baseline IIQ Social Relationships Score at 3, 6, 9, 12 Months	Continuous	The Incontinence Impact Questionnaire-Social Relationships Score will be computed at baseline and 6 months (and 3, 9, and 12 months) using the standard scoring algorithm. Specifically, instructions are to average responses across questions K, L, N, O, P, Q, R, S, W, and X (0=Not at all, 1=Slightly, 2=Moderately, 3=Greatly), and then multiply by 100/3. If any responses are missing, then the score will be calculated as the average of the non-missing responses. The outcome will then be computed as the difference in score at 6 months (and 3, 9, and 12 months) and the score at baseline. If data for an assessment time point are missing, the outcome variable will be coded as missing.				
Change from Baseline IIQ Emotional Health Score at 3, 6, 9, 12 Months	Continuous	The Incontinence Impact Questionnaire-Emotional Health Score will be computed at baseline and 6 months (and 3, 9, and 12 months) using the standard scoring algorithm. Specifically, instructions are to average responses across questions T, V, Y, Z, AA, BB, CC, and DD, (0=Not at all, 1=Slightly, 2=Moderately, 3=Greatly), and then multiply by 100/3. If any responses are missing, then the score will be calculated as the average of the non-missing responses. The outcome will then be computed as the difference in score at 6 months (and 3, 9, and 12 months) and the score at baseline. If data for an assessment time point are missing, the outcome variable will be coded as missing.				
Change from Baseline IIQ Total Score at 3, 6, 9, 12 Months	Continuous	The Incontinence Impact Questionnaire-Total Score will be computed at baseline and 6 months (and 3, 9, and 12 months) using the standard scoring algorithm. Specifically, instructions are to sum the Physical Activity, Travel, Social Relationships, and Emotional Health subscale scores of the IIQ. If any subscale scores are missing, then no Total score will be calculated. The outcome will then be computed as the difference in Total score at 6 months (and 3, 9, and 12 months) and the Total score at baseline. If data for an assessment time point are missing, the outcome variable will be coded as missing.				

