Pelvic Pain	Dichotomous 1=yes 0=no	The frequency of pelvic pain events will be taken from all adverse event reporting forms submitted for a participant. The outcome variable will be coded with a value of "Yes" if the participant had any reported pelvic pain over their study duration, identified by MEDRA coding preferred term of "Pelvic pain". If no pelvic pain events were reported for a participant, the outcome variable will be coded with a value of "No".	
Dyspareunia	Dichotomous 1=yes 0=no	The frequency of dyspareunia events will be taken from all adverse event reporting forms submitted for a participant. The outcome variable will be coded with a value of "Yes" if the participant had any reported dyspareunia over their study duration, identified by MEDRA coding preferred term of "Dyspareunia". If no dyspareunia events were reported for a participant, the outcome variable will be coded with a value of "No".	
Levator Syndrome	Dichotomous 1=yes 0=no	The frequency of levator spasm events will be taken from all adverse event reporting forms submitted for a participant. The outcome variable will be coded with a value of "Yes" if the participant had any reported levator spasms over their study duration, identified by MEDRA coding preferred term of "Levator syndrome". If no levator spasm events were reported for a participant, the outcome variable will be coded with a value of "No".	
Self-report New/worsening abdominal/genital pain (UDI item N)	Dichotomous 1=yes 0=no	Self-report of new or worsening abdominal/genital pain is captured in the UDI form item N at baseline and 6 months (and 3, 9, and 12 months). The outcome variable will be coded with a value of "Yes" if any post-baseline UDI assessment reported a worse bother than at baseline (ordered categories are "No", "Yes" with bother not specified / "Not at all", "Yes" and "Slightly", "Yes" and "Moderately, "Yes" and "Greatly"). For	

Variable	Туре	Definition	
		participants that did not have any post-baseline visits, the outcome variable will be set to missing. UDI item N: Do you experience pain in the lower abdominal or genital area?	
		Yes No (Skip to O.)	
		If yes, how much does it bother you?	
		□ Not at all □ Slightly □ Moderately □ Greatly	
Self-report New/worsening dyspareunia (PISQ item C5)			
		PISQ item C5: (completed only for sexually active)	
		How often do you feel pain during sexual intercourse? (If you don't have intercourse check this box \Box and skip to the next item.)	
		$1 \square$ Never	

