		2 □ Rarely 3 □ Sometimes	
		4 □ Usually	
		5 🗆 Always	

Variable	Туре	Definition	
Self-report New/worsening difficulty emptying bladder (UDI item J)	Dichotomous 1=yes 0=no	Self-report of new or worsening difficulty emptying bladder is captured on the UDI for item J at baseline and 6 months (and 3, 9, and 12 months). The outcome variable will coded with a value of "Yes" if any post-baseline UDI assessment reported a worse bo than at baseline (ordered categories are "No", "Yes" with bother not specified / "Not all", "Yes" and "Slightly", "Yes" and "Moderately, "Yes" and "Greatly"). For participants that did not have any post-baseline visits, the outcome variable will be se missing.	
		UDI item J:	
		Do you experience difficulty emptying your bladder?	
		Yes No (Skip to K.)	
		If yes, how much does it bother you?	
Other AEs or symptoms of interest	Dichotomous 1=yes 0=no	 We will also look to see if there are any additional AEs to report on the AE table, covering the following: These will be identified via evaluation of AE preferred terms, verbatim descriptions/comments and AE relationship at least possibly related. Other MUS surgical wound healing problems >6 weeks New/worsening vaginal infection Other infection possibly related to intervention New/worsening partner dyspareunia 	
		At final database lock review, 2 additional event terms of interest were identified: "pyelonephritis", and "Gonococcal pelvic inflammatory disease". Appropriate indicator variables will be created for each additional term of interest, coded to "Yes" if the participant has any reported events coded to the respective MEDRA preferred term. The outcome variable will be set to "No", otherwise.	

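### UDI-total, the primary endpoint, scores a wholly unanswered subscale as 0, although the SAP's IIQ and OAB-q HRQL totals become missing in the same situation

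*SAP*

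**What the plan says.** SAP section 9.2 (Variable Definitions) builds UDI-total by adding the stress, irritative and obstructive subscales. For incomplete forms it states: "If any subscale scores are missing, then the score will be calculated as the sum of the non-missing scales". There is no rescaling. The same definition serves baseline and every follow-up visit.

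Within each subscale the rule differs: "If any responses are missing, then the score will be calculated as the average of the non-missing responses". The mean is multiplied by 100/3, and a response of 0 means the symptom is absent or present without bother. The stress score uses items D and F, the irritative score uses A, B, C, G, H and I, and for the obstructive score the instruction is to "average responses across questions E, J, K, L, M, N, O, P, Q, R, and S".

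Two other totals in the same section are also built from subscales. For the IIQ: "If any subscale scores are missing, then no Total score will be calculated". For the OAB-q HRQL: "If any of the listed subscales are missing, the Total score will also be set to missing".

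SAP section 13, which lists changes from the protocol's analysis, does not mention UDI scoring.

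**The concern.** Leaving a subscale out of a sum is numerically the same as scoring it 0. Higher UDI scores are worse (protocol section 3.4.1), so non-response is recorded as the best possible result on that subscale. At follow-up this creates improvement. At baseline it understates the starting score and so hides improvement.

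The score affected is the primary outcome at 6 months and a secondary outcome at 3 months (SAP sections 3.2.1 and 3.2.2). It also feeds the subgroup analysis (7.9) and both the MID estimates and the percentage of women meeting the MID (9.5.3). A partial total counts as observed for the 10% missing-data condition in SAP sections 7.3 and 9.3, so that check would not pick it up. That analysis also requires a treatment difference before it is run.

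The sentence in section 9.2 that makes the outcome missing when data for a time point are missing does not cure this. If it covered partly completed forms, the subscale sentence would never operate.

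**Working it through.** **When the rule operates.** A subscale is missing only if all its items are blank: 2 stress, 6 irritative or 11 obstructive. The skip instructions printed for item N ("Yes No (Skip to O") and item J ("Yes No (Skip to K") indicate that the form runs in letter order. For a form abandoned part-way:

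- after A, B or C: stress and obstructive are blank;
- after D: obstructive is blank;
- after E or later: no subscale is blank.

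The only other route is to skip every item of one subscale.

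**Inputs.** ESTEEM baseline means (protocol Table 6): total 178, stress 86, irritative 66. ESTEEM sling-arm 6-month changes (protocol Table 7): total -118, stress -64, irritative -40. SD 46.5, planned difference 26 and 69 evaluable women per arm (SAP section 6). As a check on the planning figures, an exact two-sample t calculation with 26, 46.5, two-sided 0.05 and 90% power returns 69 per arm (power 90.3%), as stated.

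**Obstructive scores, by subtraction.** Baseline 178 - 86 - 66 = 26. Change -118 + 64 + 40 = -14.

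**6-month scores.** Stress 86 - 64 = 22; irritative 66 - 40 = 26; obstructive 26 - 14 = 12; total 60.

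**Recorded change with one subscale blank at 6 months:**

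| Blank subscale | Sling-like woman (true -118) | False gain | Woman with no change (true 0) |
|---|---|---|---|
| Stress | (60 - 22) - 178 = -140 | 22 | -86 |
| Irritative | (60 - 26) - 178 = -144 | 26 | -66 |
| Obstructive | (60 - 12) - 178 = -130 | 12 | -26 |

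With stress and obstructive both blank, the false gain is 22 + 12 = 34 (sling-like) or 86 + 26 = 112 (no change). The error is nil only if the true score on the blank subscale is 0, which is plausible for stress after a sling.

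**Blank at baseline.** With obstructive blank, the sling-like change is recorded as 60 - 152 = -92 instead of -118, before baseline adjustment absorbs part of the error.

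**Trial level.** One affected woman shifts her arm mean by error/69:

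- one blank subscale: from 12/69 = 0.17 to 86/69 = 1.25 points;
- two blank: 34/69 = 0.49 to 112/69 = 1.62 points.

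The standard error of the difference is 46.5 × √(2/69) = 7.92.

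**Would scaling up the answered subscales do?** For the no-change woman (true total 178), 1.5 times the two answered subscales gives:

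- stress blank: 1.5 × 92 = 138, an error of -40;
- irritative blank: 1.5 × 112 = 168, an error of -10;
- obstructive blank: 1.5 × 152 = 228, an error of +50.

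The subscale means are too unequal (86, 66, 26) for this to be safe.

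**The case against.** The strongest reply is that this hardly matters in practice. A whole subscale must be blank, no rate of partial forms is given, and nothing suggests they would cluster in one arm. To move the contrast by one standard error, about 21 sling-like women with irritative blank (7.92/0.38) or about 7 no-change women with stress blank (7.92/1.25) would all have to be in the same arm. That stands, and it limits the size of the point.

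The SAP describes its UDI scoring as the standard algorithm, and where it departs from a manual, as for the OAB-SAT-q, it says so. The rule may therefore come from the instrument. The documents do not allow this to be checked, and a published origin would not remove the arithmetic error.

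The comparison with other totals is not perfectly like for like. The OAB-q HRQL total subtracts from a fixed maximum, so a partial sum would break its scale. The SF-36 component summaries state no missing-subscale rule. The IIQ comparison is direct, and the SAP gives no reason for treating the primary endpoint differently.

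Baseline exposure is narrower than follow-up exposure. Eligibility needs answers to the UDI stress-leakage and urgency-leakage items (protocol section 4.2). If those items belong to the stress and irritative subscales, only obstructive could be blank on the initial baseline form.

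The protocol treats the MID as a between-group criterion, so comparing one woman's error with 26 is only a yardstick. Pre-lock review (SAP sections 4.5.2 and 7.6) may reveal partial forms, but the stated rule would still score them. Section 9.2 already reports some findings from lock review, so querying forms may no longer be possible. The derivation can still be changed and re-run.

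**Conclusion.** The concern holds. As written, the primary endpoint's scoring rule turns a wholly blank subscale into a score of 0. Using ESTEEM means, one blank subscale at 6 months produces a false improvement of 12 to 26 points for a sling-like woman and 26 to 86 for a woman with no change. The trial-level effect is probably small: 0.17 to 1.62 points on an arm mean per affected woman, against a standard error of about 7.9. Affected forms in both arms would partly cancel.

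These sizes rest on pooled ESTEEM baseline means combined with sling-arm changes, and on obstructive scores obtained by subtraction. No frequency of partial forms is assumed. This should be fixed because a stated primary-endpoint rule is wrong whenever it is triggered and the correction is cheap. It does not by itself threaten the trial's conclusion.

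**What to change.** Replace the subscale sentence in the UDI-total definition with: *If any UDI subscale score is missing at a visit, UDI-total for that visit is missing.* This is the rule already used for the IIQ and OAB-q HRQL totals. In addition:

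- let the MMRM handle these visits, and count them as missing for the 10% condition;
- query partial forms before lock where still possible, especially baseline and repeat baseline forms, because "for any patient who had a repeat baseline, their repeat measures will be used in the definition of baseline";
- report the number of UDI forms with a wholly missing subscale by arm and visit. Include obstructive, which is derived in section 9.2 but is not one of the three secondary outcomes in section 9.4, so comparing the n for the total with those for stress and irritative would miss it;
- if the instrument manual prescribes the current rule, keep that version as a sensitivity analysis. If the database is already locked, the count and a re-run under the new rule are still feasible.

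The cost is one SAP sentence and one line of derivation code. A few partial forms become missing, and a woman with an unresolved partial baseline form has no change score. The planned sample size does not change: losing 1, 2 or 4 six-month totals in one arm lowers power from 90.3% to 90.1%, 89.9% or 89.5%, before the MMRM recovers information from other visits.

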4.2 Inclusion Criteria

1. Reporting at least “moderate bother” from UUI item on UDI
 - a. “Do you experience urine leakage associated with a feeling of urgency?”
2. Reporting at least “moderate bother” from SUI item on UDI
 - a. “Do you experience urine leakage related to physical activity, coughing, or sneezing”
3. Diagnosis of SUI defined by a positive cough stress test (CST) or UDE within the past 18 months
If participant does not demonstrate SUI during CMG they must demonstrate SUI through a cough stress test or other comparable valsalva maneuver to be eligible.
4. Presence of UUI on bladder diary with ≥ 4 Urgency IE/3-day diary
5. Urinary symptoms ≥ 3 months
6. Persistent symptoms despite at least one or more conservative treatments (e.g. supervised behavioral therapy, physical therapy) as determined adequate by the physician.
7. Inadequate response to oral overactive bladder medications (including anti-cholinergic and/or beta-mimetic medication) unless patient is
 - a. intolerant of oral overactive bladder medications, or
 - b. oral overactive bladder medications are contraindicated as determined by the treating provider.
8. Urodynamics within past 18 months prior to enrollment or done after enrollment, prior to randomization.

9. Demonstrates understanding (or have caregiver demonstrate understanding) to perform clean intermittent self-catheterization.
Provider and patient review CISC process and patient (and/or caregiver) demonstrates understanding to the satisfaction of the provider.

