1. **Secondary urinary outcomes:** To compare treatment with Botox A to treatment with mid-urethral sling for improving the number of urinary incontinence episodes on bladder diary after 6 months. Changes from baseline in bladder diary outcomes will be calculated and analyzed using the methods described for the analysis of the primary outcome. For urinary frequency, women reporting on average >8 voids/24 hours at baseline will be considered symptomatic, and normalization of voiding frequency will be defined as ≤ 8 voids/24 hours at 6 months. A 50% improvement will be defined as a reduction by half in the number of voids that patients had at baseline. The number of women who had normalization of voiding frequency and 50% improvement at 6 months will be compared between groups separately and collectively. We will also assess the proportion of women who had worsening of urinary frequency (includes women who developed de novo frequency and those who worsened). These dichotomous outcomes will be analyzed using logistic regression, controlling for the design effects of stratification by site and age group.
2. **Predictors of poor treatment response:** To develop models to identify baseline predictors of change of MUI, OAB, and SUI outcomes measured using the UDI between baseline and 6 months post-treatment

Regression models will be created to identify predictors of change from baseline to 6 months for UDI total score and stress and irritative subscale scores. Potential predictors will include age, diary parameters such as number of UUI episodes/3 days, functional bladder capacity, stress and irritative bother severity at baseline, type of urinary incontinence (stress-predominant or urgency-predominant: see definition below), and co-existing anterior vaginal wall prolapse. The relationship between potential predictors and outcomes will be

explored in models that include one predictor plus stratification factors (site and age group). Predictive models will be constructed using backward selection of predictors. The impact of collinearity between predictors will be assessed and the final model modified as necessary.

The definition of the type of urinary incontinence, stress- or urgency predominant will be based on 2 questions of the Urogenital Distress Inventory,

1. “Do you experience urine leakage associated with a feeling of urgency?”
2. “Do you experience urine leakage related to physical activity, coughing, or sneezing?”

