Variable	Туре	Definition
Exploratory Outcomes		
Normalization of Voiding Frequency at 6 (and at 3 and 12 months)	Dichotomous (Yes/No)	The total number of daytime and nighttime voids will be taken from the bladder diary and summed and then divided by the number of diary days (<=3) to get a voiding frequency. The indicator for normalization at 6 months (and 3 and 12 months) will be defined for each subject as follows: If > 8 voids/24 hours at baseline: If > 8 voids/24 hours at time x: No If \leq 8 voids/24 hours at time x: Yes If \leq 8 voids/24 hours at baseline: Missing If data for the assessment time point are missing, the normalization indicator will be coded as missing. The variable is summarized as the percentage of participants with indicator equal to "Yes" among all non-missing indicators.
Improvement of 50% or more in Voiding Frequency at 6 months (and at 3 and 12 months)	Dichotomous (Yes/No)	The total number of daytime and nighttime voids will be taken from the bladder diary and summed and divided by the number of diary days (<=3) to get a voiding frequency. If there has been at least a 50% reduction in the voiding frequency between baseline and the time point, the improvement indicator at 6 months (and 3 and 12 months) will be set to "Yes", otherwise it will be set to "No". If data for the assessment time point are missing, the improvement indicator will be coded as missing. The variable is summarized as the percentage of participants with indicator equal to "Yes" among all non-missing indicators.
Worsening of Voiding Frequency at 6 months (and at 3 and 12 months)	Dichotomous (Yes/No)	The total number of daytime and nighttime voids will be taken from the bladder diary and summed and divided by the number of diary days (<=3) to get a voiding frequency. If there has been an increase of any amount between baseline and the time point, the worsening indicator at 6 months (and 3 and 12 months) will be set to "Yes", otherwise it will be set to "No". If data for the assessment time point are missing, the improvement indicator will be coded as missing.

Variable	Туре	Definition
		The variable is summarized as the percentage of participants with indicator equal to "Yes" among all non-missing indicators.

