Any catheter placement or intermittent self- catheterization 2 or more weeks post-procedure	Dichotomous 1=yes 0=no	The frequency of catheter placement or intermittent self-catheterization will be identified from self-catheterization (CISC) logs submitted for a participant. Additionally, adverse events that occurred 2 or more weeks after procedure reported with a "Catheter placement" action or have any text detailing self-catheterization in the comments field will also identify these cases. The outcome variable will be coded with a value of "Yes" if the participant has any reported CISC log or adverse events detailing self- catheterization, otherwise it will be coded with a value of "No".	
		Note that the Surgeon's Report form completed at time of study intervention contains questions regarding self-catheterization, but this outcome is specifically limited to timing greater than 2 weeks from study procedure.	
		Final database lock review took efforts to query sites for participants with reported self- catheterization logs or questionable post void residual results (>200mL, aside from visits immediately post-surgery) and get PI confirmation of self-catheterization in relevant adverse event comments.	
Any AE that is unexpected	Dichotomous	Participants will be coded to "Yes" if any adverse event was reported over their study	
and Related to intervention	1=yes	duration that had the following fields indicated on the form: Expected = "No"	
	0=no	Relationship = "Related"	
		Otherwise, the participant will be coded to "No".	

Variable	Туре	Definition	
Any Hospital admission or return to OR related to intervention	Dichotomous 1=yes 0=no	The frequency of hospital readmissions / returns to the operating room related to study intervention will be identified by searching for applicable terms and comments submin across all adverse events for a participant. If the participant has an event indicates hospital readmission or a return to the operating room and is reported as "Related", the indicator will be coded to "Yes", otherwise it will be coded to "No". At final database lock review, there were no adverse events reported as "related" that indicated a hospital readmission or return to the operating room.	

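### SAP 9.2 scores 50% improvement in voiding frequency in all women with a diary, including those whose baseline frequency was normal, unlike the adjacent normalization indicator

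*SAP*

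**What the plan says.** SAP 9.2 defines two neighbouring indicators from the bladder diary, each at 6 months and also at 3 and 12 months.

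- **Normalization.** Women above 8 voids/24 h at baseline are scored Yes or No according to whether they are at or below 8 at follow-up. For the rest the rule is "If \leq 8 voids/24 hours at baseline: Missing".
- **Improvement of 50% or more.** The indicator is Yes "If there has been at least a 50% reduction in the voiding frequency between baseline and the time point" and No otherwise. The only route to a missing value is a missing assessment: "If data for the assessment time point are missing, the improvement indicator will be coded as missing". The percentage is taken over all non-missing indicators.

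The protocol text behind both is in section 6.2.3, aim 1. It says that "women reporting on average >8 voids/24 hours at baseline will be considered symptomatic", and then that "A 50% improvement will be defined as a reduction by half in the number of voids that patients had at baseline". It plans a joint comparison as well as two single ones: "The number of women who had normalization of voiding frequency and 50% improvement at 6 months will be compared between groups separately and collectively".

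The diary entry criterion in Protocol 4.2 concerns urgency leakage only: "Presence of UUI on bladder diary with ≥ 4 Urgency IE/3-day diary". No minimum number of voids is required. Catheter use is a separate safety variable in SAP 9.2: "The frequency of catheter placement or intermittent self-catheterization will be identified from self-catheterization (CISC) logs submitted for a participant".

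**The concern.** Two indicators drawn from the same diary, and meant to be read together, have different denominators. A woman with 6 voids/24 h at baseline is outside the normalization analysis but inside the improvement analysis. She counts there as a failure unless she falls to 3, and at 3 she counts as a success. Neither score tells the reader about relief of frequency, because by the protocol's own threshold she had no frequency to relieve.

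Two things are at stake. First, the reported improvement percentages would understate the response among the women for whom halving is a meaningful goal, by an amount that depends on case mix. Second, the joint comparison has no defined denominator: the same woman can be missing on one component and Yes on the other.

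**Working it through.** The documents give no expected rate, power or sample size for this outcome, so there is no planned figure to reproduce. The check is of the definitions, followed by the arithmetic of dilution.

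**Step 1. Who can score Yes.** Yes requires follow-up frequency ≤ baseline ÷ 2. At the threshold of 8 this is 8 ÷ 2 = 4, so every woman at or below 8 voids/24 h at baseline must reach 4 or fewer. A woman at 6 must reach 3.

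**Step 2. Whether such women can be in the trial.** Protocol 4.2 sets no minimum frequency, and the SAP's own missing rule for normalization provides for women at or below 8. They can be present. How many is not stated.

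**Step 3. Dilution.** Let s be the share with 8 or fewer voids/24 h at baseline (taken as equal in the two arms, as randomization would lead one to expect), pS the response rate in women above 8, and pN the rate in the others. The rate as defined in the SAP is

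rate = (1 − s) × pS + s × pN.

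With pN = 0 this is (1 − s) × pS in each arm, so the risk difference is also multiplied by (1 − s), and the risk ratio is unchanged because the factor cancels.

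Illustration with assumed values pS = 30% and 15%, pN = 0:

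| s (assumed) | Rates, all women | Risk difference | Risk ratio | Odds ratio |
|---|---|---|---|---|
| 0 | 30.0% vs 15.0% | 15.0 points | 2.0 | 2.43 |
| 10% | 27.0% vs 13.5% | 13.5 points | 2.0 | 2.37 |
| 30% | 21.0% vs 10.5% | 10.5 points | 2.0 | 2.27 |
| 50% | 15.0% vs 7.5% | 7.5 points | 2.0 | 2.18 |

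For example, at s = 50% the odds ratio is (0.15/0.85) ÷ (0.075/0.925) = 2.18.

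If instead 2% of the normal-frequency women respond in both arms, the risk differences are the same and the odds ratio at s = 50% is 2.05, from rates of 16.0% and 8.5%.

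**Step 4. Power, for scale only.** With the 69 evaluable women per arm from Protocol 6.1.1 and s = 30%, power for this illustration is about 39% with all women and about 42% with only the symptomatic women (69 × 0.7 ≈ 48 per arm). The restriction neither costs nor gains much power.

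**Step 5. Catheter use, as a separate matter.** Protocol Table 4 gives intermittent catheterization after 100 units in one earlier trial as 5% at 2 months, 3% at 4 months and 1% at 6 months, and catheter use after sling in another as 2% beyond 2 weeks. On 69 women:

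- Botox at 6 months: 0.01 × 69 = 0.7 women.
- Botox around 3 months: 0.03 × 69 = 2.1 to 0.05 × 69 = 3.5 women.
- Sling beyond 2 weeks: 0.02 × 69 = 1.4 women.

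These count women catheterizing. They are ceilings for misclassification from this source, since a catheterizing woman need not have halved her recorded voids.

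**The case against.** The strongest reply is that the SAP follows the protocol. Protocol 6.2.3 defines 50% improvement relative to each patient's own baseline and does not restrict it to symptomatic women. Normalization has to exclude women already at or below 8, whereas a relative reduction can be computed for anyone. The worsening indicator in SAP 9.2 also uses all women. This stands in part: the wording is a weakness shared with the protocol, not a demonstrated departure from it. It does not make a fall from 6 to 3 voids a meaningful success, nor does it supply a denominator for the joint comparison.

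A second reply is that SAP 9.4 compares repeated dichotomous outcomes by an odds ratio adjusted for baseline value, site and age group. If baseline value there means baseline voiding frequency, part of the problem is absorbed in the odds ratio. That also stands, but the adjustment does not touch the reported percentages.

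A reader might go further and infer that including normal-frequency women is what allows retention or catheter use to pass as improvement, to the advantage of the Botox arm. The documents do not support this. A woman above 8 voids/24 h can also halve her recorded voids through retention, and the same route exists for normalization, so the baseline condition neither creates it nor closes it. The Botox figures in Table 4 are ceilings and have to be set beside the 2% after sling. A second Botox injection between 3 and 6 months could raise the 6-month figure, but the documents give no number for that. Retention, residual urine volume, catheter use and self-reported difficulty emptying are also reported by arm, so such harm would not be hidden.

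**Conclusion.** The point holds as a narrow defect of definition. The 50% indicator lacks the baseline condition carried by its neighbour, so its percentage mixes women who had frequency to improve with women who did not.

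Its size rests on s, which the documents do not give. Over an assumed 10% to 50%, and if no normal-frequency woman responds, the rates and the risk difference fall to between 0.9 and 0.5 of their values in symptomatic women. The comparison between arms is far less affected: under that assumption the risk ratio does not move and the odds ratio moves modestly. It would be wrong to infer that the comparison is biased toward one treatment, or that a particular number of percentage points is lost, because both the share and the true response rates are unknown.

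The outcome is exploratory, and its p-values are descriptive under Protocol 6.2.3 and SAP 7.8. No primary or secondary conclusion changes. This is a cheap improvement, not a serious flaw.

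**What to change.** In SAP 9.2, set the 50% improvement indicator to missing when baseline frequency is 8 or fewer voids/24 h, as is already done for normalization. State that the joint comparison with normalization uses this same denominator. The restriction uses only a baseline diary value, so the randomized comparison is preserved. The cost is one line of text and a smaller denominator for one exploratory outcome.

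Separately, and only as an optional check, the SAP could say how catheterizations are counted in the diary, which neither document does. It could then repeat both indicators with women who were catheterizing when the diary was kept, as identified from the self-catheterization logs, counted as not improved and not normalized. This is one of several defensible ways to handle such women, so it belongs in a sensitivity analysis and not in the main definition. The logs are already collected, and few women are likely to be affected in either arm.
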